7.6. Cardiac Safety Monitoring

7.7. Cardiac safety monitoring should be done based on symptomatology and at Investigator's discretion. Tumor Response Assessments

Tumor response assessments will be performed per standard of care.

Imaging studies will include a computerized tomography (CT) or magnetic resonance imaging (MRI) scan of the brain, chest, abdomen, pelvis. For subjects diagnosed with primary brain tumors, only the MRI of the brain will be required at Screening and during the study.

Tumor assessments will include all known or suspected disease sites and will be performed per specified timepoints according to the Schedules of Activities. For all tumor assessments, the method of assessment that was used at Screening should be the same method used throughout the study.

For all subjects, radiographic confirmation of objective tumor response or disease progression will be based on RECIST v1.1 and assessed locally.

Subjects discontinuing study treatment before documented radiographic progression will complete an EOT visit and safety follow-up visit per Section 8.4.

For subjects discontinuing the study treatment due to documented radiographic progression survival status will be obtained via a phone call or medical chart review, including information about subsequent anticancer therapies (including best response) every three months until death, loss of follow-up, or withdrawal of consent, whichever comes first.

8. STUDY CONDUCT

Scheduled protocol-related activities will be performed at specified timepoints and within windows as outlined in the Schedule of Activities for Dose Escalation (Table 1). If a visit is missed for any reason, the next scheduled visit should occur as originally planned.

8.1. Screening And Eligibility

All patients being considered for the study and are eligible for screening must provide informed consent for the study prior to completing any study-specific procedures (up to 28 days prior to initial dose). A patient number will be assigned. Subjects will be screened within 28 days prior to the administration of TPX-0046 to confirm that they meet the eligibility criteria. Subjects participating in the Phase 1 Dose Escalation, Dose Expansion (QD, BID, and and Food effect Sub-study must have eligibility confirmed

The following items must be completed as part of the screening procedures:

- Eligibility checklist (see complete list in Sections Section 5.1 and Section 5.2) must be completed for each subject and sent to the Sponsor for eligibility confirmation before enrollment
- Source documents for molecular pathology report, detailing the specific test that confirms *RET* gene fusion, should be submitted for the Sponsor's approval of eligibility

• Imaging studies (CT or MRI of the chest, abdomen, and pelvis and MRI of the brain) should be submitted and confirmed by BICR (Phase 2 only)

8.2. Timing of Clinical Procedures

On visits that require in-clinic dosing, clinical assessments should be conducted as described in Table 1.

8.3. Study Duration

Subjects will remain on study treatment until disease progression, development of unacceptable toxicity, the ability to move to alternative care is identified, or withdrawal of consent.

8.4. Subject Treatment Discontinuation

Subjects discontinuing the study treatment prior to documented radiographic progression will complete an EOT visit (Section 8.5) and safety follow-up visit (Section 8.6).

8.5. End of Treatment Visit

For subjects who discontinue study drug, the EOT visit should occur as soon as possible (within 7 days) after the last dose of investigational product.

8.6. Safety Follow-up Visit

The safety follow-up visit should occur approximately 28 days after the last dose or before any new anticancer treatment is started.

8.7. Subject Discontinuation and Withdrawal from Study

A subject may be discontinued from study treatment at any time if the subject, the Investigator, or the Sponsor Medical Monitor determine that it is not in the subject's best interest to continue on study. The following is a list of possible reasons for early discontinuation of study treatment:

- Disease progression (treatment beyond radiographic or clinical progression will not be allowed)
- Any adverse event that cannot be adequately managed with dose modifications, including dose interruption > 28 days (unless there is reasonable evidence of clinical benefit to justify continuation on the protocol which must be previously discussed with Turning Point Therapeutics)
- Protocol violation requiring discontinuation of study treatment
- Subject is not compliant with study procedures
- Lost to follow-up
- Subject withdrawal of consent for further treatment
- Investigator identifies alternative treatment option for the patient
- Turning Point Therapeutics' early termination of study. Reasons for terminating the study may include, but are not limited to, the following:

- All enrolled subjects have discontinued study treatment
- The incidence or severity of AEs in this or other studies indicates a potential health hazard to subjects
- Subject enrollment is unsatisfactory

Data to be collected for the EOT visit are described in the Schedules of Assessments.

Subjects will be followed for at least 28 calendar days after the last dose of TPX-0046. If a subject is discontinued from treatment due to an AE, the subject will be followed until the AE has resolved or stabilized as per Section 9.3.4.

8.7.1. Withdrawal of Consent

A subject may withdraw consent for any further contact with him or her or persons previously authorized by the subject to provide this information. Subjects should notify the Investigator in writing of the decision to withdraw consent from future follow up, whenever possible. The withdrawal of consent should be explained in detail in the medical records by the Investigator, as to whether the withdrawal is only from further receipt of the investigational product or also from study procedures and/or posttreatment study follow up and entered on the appropriate CRF page. If vital status (whether the subject is alive or dead) is being measured, publicly available information should be used to determine vital status only as appropriately directed in accordance with local law.

8.7.2. Lost to Follow-up

All reasonable efforts must be made to locate subjects to determine and report their ongoing status. This includes follow up with persons authorized by the subject as noted above. Lost to follow up is defined by the inability to reach the subject after a minimum of 2 documented phone calls, faxes, or e mails as well as lack of response by the subject to 1 registered mail letter. All attempts should be documented in the subject's medical records. If it is determined that the subject has died, the site will use locally permissible methods to obtain the date and cause of death. If the Investigator's use of a third-party representative to assist in the follow-up part of the study has been included in the subject's informed consent, then the Investigator may use a Sponsor retained third-party representative to assist site staff with obtaining the subject's contact information or other public vital status data necessary to complete the follow-up part of the study. The site staff and representative will consult publicly available sources, such as public health registries and databases, to obtain updated contact information. If, after all attempts, the subject remains lost to follow up, then the last known alive date as determined by the Investigator should be reported and documented in the subject's medical records.

If a subject does not return for a scheduled visit, every effort should be made to contact the subject. All attempts to contact the subject and information received during contact attempts must be documented in the subject's medical record. In any circumstance, every effort should be made to document subject outcome, if possible. The Investigator should inquire about the reason for withdrawal, request that the subject return all unused investigational product, request that the subject return for a final visit, if applicable, and follow up with the subject regarding any unresolved AEs.

If the subject refuses further visits, no further study-specific evaluations should be performed, and no additional data should be collected. The Sponsor may retain and continue to use any data collected before such withdrawal of consent.

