9.3.4. Follow-up of Adverse Events and Serious Adverse Events

All AEs must be followed until the AE resolves, is no longer of clinical concern, has stabilized or is otherwise explained, or the subject is lost to follow-up.

AEs ongoing at the final follow-up assessment that are deemed to be "related" to the investigational product or of other clinical significance must be followed for as long as necessary to adequately evaluate the safety of the subject or until the event stabilizes, resolves, or is no longer of clinical concern. If resolved, a resolution date for the AE should be documented in the CRF. The Investigator must ensure that follow-up includes any supplemental investigations indicated to elucidate the nature and/or causality of the AE. This may include additional laboratory tests or investigations, or consultation with other healthcare professionals, as considered clinically appropriate by the Investigator.

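### Section 8.7.2 ends all data collection when a subject declines visits, in conflict with the adverse event follow-up required by 8.7 and 9.3.4

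*Combined protocol and SAP*

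**What the plan says.** The rule closes Section 8.7.2 (Lost to Follow-up): "If the subject refuses further visits, no further study-specific evaluations should be performed, and no additional data should be collected." The next sentence reads: "The Sponsor may retain and continue to use any data collected before such withdrawal of consent." The section thus equates declining visits with withdrawing consent.

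Other sections bear on the same subject:

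- **8.7.1 (Withdrawal of Consent)** has the investigator explain in the medical records and enter on the CRF "as to whether the withdrawal is only from further receipt of the investigational product or also from study procedures and/or posttreatment study follow up".
- **8.7** sets a minimum: "Subjects will be followed for at least 28 calendar days after the last dose of TPX-0046." It adds: "If a subject is discontinued from treatment due to an AE, the subject will be followed until the AE has resolved or stabilized."
- **9.3.4** states: "All AEs must be followed until the AE resolves, is no longer of clinical concern, has stabilized or is otherwise explained", with one exit that depends on the subject's status: "or the subject is lost to follow-up".
- **9.3.1 and 9.3.2** collect AEs and serious AEs (SAEs) from first dose to 28 days after last dose.
- **8.7.2, preceding paragraph**, tells the site to try to document the outcome whatever the circumstances, and to ask about unresolved AEs.

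**The concern.** Declining clinic visits is not the same as refusing all contact. A subject may say no to further visits and still accept a telephone call or a look at the chart. For that subject, 8.7.2 tells the site to stop, while 8.7 and 9.3.4 tell it to continue.

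Safety and tolerability is a primary objective (Section 3). Subjects who stop attending could be those with open AEs. That is a plausible inference; the documents do not report it. If a site applies 8.7.2 literally, the onset or worsening of non-fatal AEs within the 28-day window, and the outcome of AEs already open, may not reach the database.

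**Working it through.** The documents state no figure on this point, so there is nothing to reproduce. The check is a comparison of the text, followed by a simple illustration of scale.

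**Step 1. Which rule applies to a reachable subject who declines visits only?**

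| Section | Instruction | Exit that this subject meets |
|---|---|---|
| 8.7.2, last paragraph | Stop evaluations and data collection | Refusal of visits is itself the trigger |
| 8.7 | Follow at least 28 days; after an AE discontinuation, until the AE resolves or stabilizes | None stated |
| 9.3.4 | Follow all AEs to an endpoint of the event, or until loss to follow-up | None, because the subject can be reached |
| 9.3.1, 9.3.2 | Collect AEs and SAEs to 28 days after last dose | None stated |
| 8.7.1 | Document the scope of withdrawal | Not an exit; asks a question that 8.7.2 skips |

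Section 8.7.2 itself defines loss to follow-up as inability to reach the subject after a set number of attempts. Someone who answers and declines visits does not meet that definition. The conflict with 8.7 and 9.3.4 is therefore direct. The conflict with 8.7.1 is only by implication: it separates levels of withdrawal but does not say which data continue at each level.

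**Step 2. Direction of any effect.** The Safety Analysis Set keeps every dosed subject (10.1.3). AE incidence is reported as frequency and percentage, at maximum severity per subject (10.3.5.2). Missing data are generally not imputed (10.3.1.2). From these three rules I infer that a subject whose later AE was not collected stays in the denominator without it, or stays at a lower grade. The protocol does not say this outright. On that reading, lost collection can only lower incidence and severity, while outcomes of open AEs stay incomplete.

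**Step 3. Scale, as illustration only.** Inputs: 41 subjects enrolled across 9 dose levels (10.2.1). The number of refusers is not given; 1, 2 and 4 are assumed here.

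- Overall, k subjects with an uncollected event: k/41. For k = 1, 1/41 = 2.4 percentage points; for k = 2, 4.9; for k = 4, 9.8.
- Mean subjects per level: 41/9 = 4.6. One subject in an average level: 1/(41/9) = 9/41 = 22 percentage points.
- Actual cohort sizes are not given. If a level held 6 or 3 subjects (assumed), one subject would be 1/6 = 17 or 1/3 = 33 points.

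These figures show what one subject weighs. They do not estimate bias.

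**The case against.** The strongest defense is that the sentence after the rule speaks of withdrawal of consent. If the rule is meant only for subjects who withdraw consent to all contact, stopping is proper. It is also possible to read 8.7.2 as a sequence: a visit is missed, the site makes contact and asks about open AEs, and collection stops only if the subject then refuses. Both readings are fair, but neither removes the conflict. The trigger as written is refusal of visits, and asking once about open AEs is not following them to resolution or through 28 days.

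Other parts of the defense stand and limit the point. A reader might infer more than the documents support in five ways:

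- **That deaths go unrecorded.** Section 9.3.3 requires all deaths on the Death CRF, 8.7.1 allows public vital-status sources subject to local law, and 8.7.2 tells sites to obtain date and cause once a death is known.
- **That later serious events are wholly lost.** Section 9.3.2 still requires notification of a possibly attributable SAE that the investigator learns of even after the study ends. This offsets the gap in part.
- **That 8.7.1 says the opposite of 8.7.2.** It only requires the scope to be documented.
- **That remote AE collection is already established.** Section 7.7 provides that "survival status will be obtained via a phone call or medical chart review", but only after documented radiographic progression, and for survival and later therapy. It shows that such contact is feasible, not that it is an agreed AE source.
- **That the first-cycle DLT endpoint is biased in the same way.** Under 4.1.1.2, a subject with no DLT who took less than 75% of expected doses is not evaluable for DLT. An early refuser of this kind drops out of that assessment and is not counted as free of DLT.

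The practical reach is also small. Enrollment is closed, development has stopped, and a synoptic study report is planned.

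**Conclusion.** The inconsistency is real and can be seen from the text alone. Section 8.7.2 stops collection on a trigger that 8.7 and 9.3.4 do not recognize as an exit, and it skips the question of scope that 8.7.1 requires. The consequence is conditional: for a reachable subject who declines only visits, non-fatal AE onset, worsening or outcome after the refusal may go uncollected, which can understate AE incidence and severity.

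The size cannot be determined without the number of refusers and the cohort sizes, so the per-subject percentages must not be read as expected bias. Nor do the documents show that anyone has refused visits because of toxicity or that data have been lost. The effect now concerns mainly late follow-up of subjects still on study. They will all come off treatment, which is when these follow-up rules matter, so a clarification is still worth making.

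**What to change.** Reconcile 8.7.2 with 8.7, 8.7.1 and 9.3.4:

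- Limit the bar on further data to subjects who withdraw consent for follow-up or contact, as documented under 8.7.1.
- For subjects who decline visits only, state that AEs (with outcome) and vital status continue to be collected by telephone or chart review through 28 days after last dose.
- State that ongoing AEs are followed under 9.3.4, as far as the subject's consent allows.

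The cost is a short protocol clarification and a little site effort for calls or chart checks. Withdrawal of consent for all contact remains fully respected.

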9. ADVERSE EVENT REPORTING

Adverse event assessments will be performed at times specified at each clinic visit as specified in the Schedules of Activities:

Events that are clearly consistent with the expected pattern of progression of the underlying disease should not be reported as an AE or serious adverse event (SAE). Radiographic progression according to RECIST v1.1 criteria should be documented to support disease progression. If there is any uncertainty as to whether an event is due to disease progression, it should be reported as an AE.

Adverse events will be graded according to CTCAE version 5.0. The type, incidence, severity, timing, seriousness, and relatedness of AEs and laboratory abnormalities will be reported.

9.1. Adverse Events, Serious Adverse Events, and Anticipated Serious Adverse Events

9.1.1. Definition of Adverse Events

An AE is defined as any untoward medical occurrence in a subject or clinical investigation subject administered a pharmaceutical product and which does not necessarily have a causal relationship with this treatment.

An AE can, therefore, be any unfavorable and unintended sign (including an abnormal laboratory finding, for example), symptom, or disease temporally associated with the use of a medicinal product, whether considered related to the medicinal product. For this study, AEs will be recorded starting at the time of first administration of the investigational product through the last follow-up visit for all dose levels/cohorts.

AEs include, but are not limited to, (1) a worsening or change in nature, severity, or frequency of condition(s) present at the start of the study; (2) subject deterioration due to primary illness; (3) intercurrent illness; and (4) drug interaction. For recording purposes, pregnancy in the partner of a healthy male subject is a medical condition and is not considered an AE.

Subjects should be questioned in a general way, without leading the subject or asking about the occurrence of any specific symptom.

The Investigator should attempt to establish a diagnosis of the event based on signs, symptoms, and/or other clinical information. The diagnosis and not the individual signs/symptoms should be documented as the AE. For example, if the underlying disease process is a gastric ulcer, it would not be appropriate to record the AE by describing the symptoms "stomach pain," "indigestion," or "appetite loss". The AE medical term of "gastric ulcer" should be recorded as the AE.

9.1.2. Definition of Serious Adverse Events

A serious AE (SAE) (an experience or a reaction) is an AE that leads to one or more of the following:

- Death An AE that causes or contributes to a fatal outcome
- Is life-threatening Refers to an event/reaction, in the view of the Investigator, places the subject at immediate risk of death. It does not refer to an event/reaction that hypothetically might cause death if it were more severe
- Requires inpatient hospitalization or prolongation of existing hospitalization, except for the following:
 - Hospitalization for respite care or social admissions (eg, lack of housing, economic inadequacy, family circumstances)
 - Hospitalization solely for coordination of care, including hospice arrangements
 - Hospitalization due solely to progression of the underlying cancer
 - Hospitalization that was necessary solely because of subject requirement for outpatient care outside of normal outpatient clinic operating hours
 - Hospitalization for same day surgeries (as outpatient/same day/ambulatory procedures)
 - Planned hospitalization required by the protocol (eg, for study drug administration or insertion of access device for study drug administration)
 - Hospitalization for a preexisting condition, provided that the hospitalization was
 planned prior to the study or was scheduled during the study when elective
 surgery became necessary because of the expected normal progression of the
 disease and the subject has not experienced an adverse event
- Results in persistent or significant disability/incapacity (ie, the adverse event results in substantial disruption of the subject's ability to conduct normal life functions)
- Congenital anomaly/birth defect
- Important medical events, when based upon appropriate medical judgment, may jeopardize the subject and may require medical or surgical intervention to prevent one of the outcomes listed above

9.1.3. Definition of Anticipated Serious Adverse Events

Anticipated SAEs are SAEs that could be anticipated due to the underlying metastatic disease in the population being studied in this clinical trial. This list of possible anticipated SAEs by the Medical Dictionary for Regulatory Activities (MedDRA) Preferred Terms was adapted from Hyde, 1974; Chute, 1985; and Silvestri, 1995.

- Cough
- Abnormal loss of weight
- Weight decreased
- Dyspnoea
- Chest pain

- Neck pain
- Hemoptysis
- Cancer pain
- Bone pain
- Dysphonia
- Musculoskeletal pain
- Headache
- Muscular weakness
- Lymphadenopathy
- Malignant neoplasm

9.2. Relationship to the Investigational Product

The Investigator will document his or her opinion of the relationship of the AE to treatment with the investigational product using the criteria outlined in Table 12. A "reasonable possibility" that the investigational product caused the AE means there is evidence to suggest a causal relationship between the investigational product and the AE.

If the relationship between the AE/SAE and the investigational product is determined to be "possible" or "probable," the event will be considered related to the investigational product.

Table 12: Relationship of Adverse Events to Investigational Product

Relationship	Description
Related	 A clinical event, including a laboratory test abnormality, with a reasonable time sequence to administration of the investigational product, unlikely to be attributed to concurrent disease or other drugs or chemicals, and which follows a clinically reasonable response on withdrawal (de-challenge) An event that could also be explained by concurrent disease or other drugs or chemicals where information on investigational product withdrawal may be lacking or unclear Re-challenge or de-challenge information is not required to fulfill this definition
Not Related	 4. A clinical event, including a laboratory test abnormality, with sufficient evidence to accept that there is no causal relationship to investigational product administration (eg, no temporal relationship to investigational product administration, because the investigational product was administered after the onset of the event; investigation shows that the drug was not administered; proof of other cause) 5. An event with a temporal relationship to investigational product administration, which makes a causal relationship improbable, and other drugs, chemicals, or underlying disease provide plausible explanations

Adverse events will be assessed using CTCAE version 5.0. AEs must be assessed for severity (mild, moderate, severe, life-threatening, or fatal), and must be entered on the AE page of the eCRF. The CTCAE version 5.0 grade refers to the severity of the AE. The CTCAE version 5.0 grading system and severity assessments are described in Table 13. It should be noted that the

term "severe" is used to grade intensity and is not synonymous with the term "serious." The assessment of severity is made regardless of the investigational product relationship or the seriousness of the AE.

Table 13: Severity of Adverse Events

Grade	Severity
1	Mild; asymptomatic or mild symptoms; clinical or diagnostic observations only; or intervention not indicated
2	Moderate; minimal, local, or non-invasive intervention indicated; or limiting age- appropriate instrumental activities of daily living ^a
3	Severe or medically significant, but not immediately life-threatening; hospitalization or prolongation of hospitalization indicated; disabling; or limiting self-care activities of daily living ^{bc}
4	Life-threatening consequences or urgent intervention indicated ^d
5	Death related to adverse event ^d

^a Instrumental activities of daily living refer to preparing meals, shopping for groceries or clothes, using the telephone, managing money, etc.

